### **7.3. MEDICAL HISTORY AND CONCOMITANT DISEASES**

Significant medical and psychiatric history, including dates of diagnoses and procedures and whether the condition is ongoing, if applicable, will be collected. Each condition will be recorded as a verbatim term, date of onset, date resolved, and a checkbox that indicates ongoing conditions. Significant surgical and medical history will be coded using the Medical Dictionary for Regulatory Activities (MedDRA) Version 20.1.

Medical and surgical history will be summarized for the safety analysis set by treatment group, system organ class (SOC), and MedDRA preferred term (PT). Patient data will be listed.

### **7.4. MEDICATION**

Any prior therapy, medication, or procedure a patient has had within 3 months before study drug administration will be recorded on the case report form (CRF). Medications will be coded according to the WHO Drug Version: June 2017. Preferred drug name, Anatomical/ Therapeutic/ Chemical (ATC) class will be reported for inclusion in the database.

Medication summaries based on ATC level 3 and the preferred drug names will be produced for the safety analysis set. The summaries will present, by treatment group, the frequency and percentage of patients who used any medication in an ATC class, or any medication based on a single preferred drug name. Medication summaries will be sorted by descending total frequency of ATC class and by PT within ATC class. Patients will be counted only once for each medication class and each preferred drug name.

#### **7.4.1. Prior Medication**

Prior medications and therapies will include all medications and therapies stopped before the first day of study drug administration. Prior medication will be summarized by the ATC level 3 and preferred name. Prior medication will be summarized. The same summary will be repeated for

prior antidepressant and ADHD medication use. These medications are identified by the ATC codes of:

ADHD medications:

N-NERVOUS SYSTEM

N06-PSYCHOANALEPTICS

N06B-PSYCHOSTIMULANTS, AGENTS USED FOR ADHD AND NOOTROPICS

N06BA-Centrally acting sympathomimetics

N06BC-Xanthine derivatives

N06BX-Other psychostimulants and nootropics.

Antidepressant:

N-NERVOUS SYSTEM

N06-PSYCHOANALEPTICS

N06A-ANTIDEPRESSANTS

N06AA-Non-selective monoamine reuptake inhibitors

N06AB-Selective serotonin reuptake inhibitors

N06AF-Monoamine oxidase inhibitors, non-selective

N06AG-Monoamine oxidase A inhibitors

N06AX-Other antidepressants.

#### **7.4.2. Other Therapies**

Prior non-pharmacological treatment will be collected in CRF. Type of treatment/procedure and indication will be listed.

Prior treatment given for TS will be summarized. The table will include number of patients with previous treatment given for TS, total duration of treatment, and best response to treatment. For an ongoing treatment, date of informed consent will be used to compute duration.

## 8. EFFICACY

The mITT analysis set will be used for all efficacy analyses, unless otherwise noted. Analyses and summaries will be presented by treatment group.

Week 13 efficacy data will be summarized but will not be included in any statistical analyses.

### 8.1. EFFICACY ASSESSMENT AND TIME POINTS

#### 8.1.1. Yale Global Tic Severity Scale (YGTSS)

The YGTSS rating scale is a semi-structured clinician rating instrument that provides an evaluation of the number, frequency, intensity, complexity, and interference of motor and phonic tics (Leckman et al 1989). The YGTSS is composed of 11 items: 5 items for motor tic severity, 5 items for vocal tic severity, and 1 item for impairment. Each item for motor tic severity and vocal is rated on a 6-point scale (0 for none to 5 to severe). The MTSS is the sum of the 5 items for motor tic severity and the VTSS is the sum of the 5 items for vocal tic severity. The TTS is the sum of the MTSS and the VTSS. The impairment score ranges from 0 (none) to 50 (severe). The GSS is the sum of the TTS and the impairment score.

YGTSS is administered at screening, baseline; and weeks 2, 4, 6, 9, 12, and 13.

For YGTSS, if a response to 1 item is missing within the MTSS or VTSS subscale, the missing response will be replaced with the average of the remaining responses within the subscale; if responses to 2 or more items within a subscale are missing, the missing responses will not be replaced and the subscale score will be set to missing; if at least 1 subscale is missing then the TTS will be set to missing. If the TTS or impairment score are missing, then the GSS will be set to missing.

#### 8.1.2. Tourette Syndrome-Clinical Global Impression (TS-CGI)

The TS-CGI is administered at baseline and at weeks 2, 4, 6, 9, 12, and 13. The TS-CGI scale is a 7-point Likert scale that allows the clinician to use all available information to assess the impact of tics on the patient's quality of life. The TS-CGI is rated as follows: 1 (normal), 2 (borderline), 3 (mild), 4 (moderate), 5 (marked), 6 (severe), and 7 (extreme).

#### 8.1.3. Tourette Syndrome-Patient Global Impression of Impact (TS-PGII)

The TS-PGII is administered at baseline and weeks 2, 4, 6, 9, 12, and 13. Input from the caregiver/adult is permitted.

The TS-PGII is a single-item questionnaire that asks the patient to assess the degree of impact due to current tics. The TS-PGII uses a 5-point scale, ranging from not at all (1) to very much (5), to assess overall response to therapy. In general, patient-rated global measures of change have face validity and have been shown to correlate with disability for a number of chronic conditions.

#### **8.1.4. Child and Adolescent Gilles de la Tourette Syndrome – Quality of Life (C&A-GTS QOL)**

The C&A-GTS-QOL is administered at baseline, week 6, and week 12. Children 13 years of age and under may be interviewed separately or jointly with the caregiver/adult as appropriate or defined by the scale. For children over 13 years of age, caregiver/adult involvement is strongly encouraged. Questions should be directed to the child, but the caregiver/adult should be encouraged to add relevant information.

The C&A-GTS-QOL is a 27-item questionnaire specific to TS patients that asks the patient to assess the extent to which their quality of life is impacted by their symptoms. The C&A-GTS-QOL contains 6 subscales (cognitive, coprophenomena, psychological, physical, obsessive-compulsive, and ADL) and uses a 5-point Likert scale ranging from no problem to extreme problem. Patients will also be asked how satisfied they feel overall with their life at that moment by using a VAS scale between 0 and 100 ([Su et al 2017](#)). Following are the questions assessed in each C&A-GTS-QOL subscale:

- Cognitive (questions 11, 12, 13, 14, 18, 20, 21, 23) (range: 0- 32)
- Psychological (questions 15, 16, 17, 19, 25, 27) (range: 0 – 24)
- Obsessive-compulsive (questions 7, 8, 9, 10) (range: 0 – 16)
- Physical (questions 1, 3, 4) (range: 0 – 12)
- Coprophenomena (questions 5, 6, 22) (range: 0 -12)
- ADL (questions 2, 24, 26) (range: 0-12)

Scores for the six subscales are generated by summing items and, for ease of interpretation, transformation to a range of 0 to 100 ( $100 \times [(observed\ score - min\ possible\ score) / (max\ possible\ score - min\ possible\ score)]$ ). The total score, resulting from the sum of the subscale scores, is also normalized to a 0-100 range. For C&A-GTS-QOL, if a response to 1 question is missing within the subscale, the missing response will be replaced with the average of the remaining responses within the subscale; if responses to 2 or more questions within a subscale are missing, the missing responses will not be replaced and the subscale score will be set to missing; if at least 1 subscale is missing then the total score will be set to missing. For all analysis and summary, transformed scores will be used.

**8.1.5.**

[REDACTED]

[REDACTED]

[REDACTED]

[REDACTED]

**8.1.6.**

[REDACTED]

[REDACTED]

[REDACTED]

**8.2. PRIMARY EFFICACY ENDPOINT AND ANALYSIS****8.2.1. Primary Efficacy Analysis**

The primary analysis will be a mixed-model, repeated-measures with the change in the TTS as the dependent variable. The model will include fixed effects for treatment group, week (5 levels: weeks 2, 4, 6, 9, and 12), and the treatment group by week interaction. The baseline TTS, region, and age group at baseline (2 levels: 6-11 year, 12-16 years) will be included as covariates. The unstructured covariance matrix for repeated observations within patients will be used. In case that the model does not converge, the Maximum-Likelihood estimation method will be used instead of the default Restricted Maximum-Likelihood. If the model still does not converge, then a simpler covariance structure with fewer parameters will be used, according to the following order: Heterogeneous Autoregressive (1), Heterogeneous Compound Symmetry, Autoregressive (1), and Compound Symmetry. The Kenward-Roger approximation will be used to estimate denominator degrees of freedom.

The least squares means of the change in TTS from baseline at week 12 will be compared (the TEV-50717 arm and the placebo arm) using a 2-sided test at the alpha=0.05 level of significance. The SAS code for this test is as follows:

[REDACTED]

The least square (LS) mean and standard error for the treatment groups, and the LS mean difference, 95% confidence interval (CI), and p-value for the comparison (TEV-50717 vs. placebo at week 12) will be presented.

Cohen's d effect size will also be computed for each comparison (Kelley, 2007). Cohen's d is calculated as:

$$d = (\mu_t - \mu_p) / (\text{pooled SD}),$$

where  $\mu_t$  represents the least-square (LS) mean of the TEV-50717 group,  $\mu_p$  is the LS mean of the placebo group, and the pooled SD is based on the adjusted LS means and adjusted standard errors from the mixed-effect model for MMRM, specifically:

$$\text{Pooled SD} = \frac{\text{Standard Error (SE)}}{\sqrt{\frac{1}{nt} + \frac{1}{np}}}$$

and  $nt$ =number of patients in TEV-50717 group and  $np$ =number of patients in placebo group.

The utility of Cohen's d is to help judge the clinical importance of a measured treatment difference.

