3.3.1. Primary Efficacy Measure and Time Points

YGTSS (to calculate TTS): Screening; baseline; and weeks 2, 4, 6, 9, 12, and 13.

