9.1. Sample Size and Power Considerations

It is estimated that approximately 58 patients per arm will enable a power of at least 90% to detect a beneficial standardized effect of 63% or more when the TEV-50717 arm is compared to placebo (difference of 6.0 in the change from baseline to week 12 in TTS, assuming a standard deviation of 9.5 in each arm) in a 2-sided type I error rate of 5% after accounting for potential dropouts.

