9.5.4.1. Primary Efficacy Analysis

The primary analysis will be a mixed-model, repeated-measures with the change in the TTS as the dependent variable. The model will include fixed effects for treatment group, week (5 levels: weeks 2, 4, 6, 9, and 12), and the treatment group by week interaction. The baseline TTS, region, and age group at baseline (2 levels: 6 to 11 years, 12 to 16 years) will be included as covariates. The unstructured covariance matrix for repeated observations within patients will be used. In case that the model does not converge, the Maximum-Likelihood estimation method will be used instead of the default Restricted Maximum-Likelihood. If the model still does not converge, then a simpler covariance structure with fewer parameters will be used, according to the following order: Heterogeneous Autoregressive (1), Heterogeneous Compound Symmetry, Autoregressive (1), and Compound Symmetry. The least squares means of the change in TTS from baseline at week 12 will be compared (the active treatment arm and the placebo arm) using a 2-sided test at the alpha=0.05 level of significance.

In addition, actual values and changes in the TTS from baseline to each visit will be summarized using descriptive statistics.

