## 3.6. TREATMENT ASSIGNMENT & BLINDING

This is a randomized, double-blind, placebo-controlled study. Patients will be randomly assigned to receive treatment with TEV-50717 or matching placebo in a 1:1 ratio stratified by age at baseline (6 to 11 years, 12 to 16 years). Patients and investigators will remain blinded to treatment assignment during the study.

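### As described, the primary MMRM fits one baseline-TTS slope to weeks 2 to 12; adding baseline by week is a cheap and usually small gain in precision at week 12

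*SAP*

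**What the plan says.** SAP 8.2.1 and Protocol 9.5.4.1 describe the same model for change in TTS. It has treatment, week (five levels) and treatment by week, with an unstructured within-patient covariance. The SAP then says "The baseline TTS, region, and age group at baseline (2 levels: 6-11 year, 12-16 years) will be included as covariates", and the Protocol says "The baseline TTS, region, and age group at baseline (2 levels: 6 to 11 years, 12 to 16 years) will be included as covariates". Neither text names an interaction of baseline with week. The confirmatory result is the week-12 difference alone, tested "using a 2-sided test at the alpha=0.05 level of significance".

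Protocol 3.3.1 sets the visits: "YGTSS (to calculate TTS): Screening; baseline; and weeks 2, 4, 6, 9, 12, and 13". Every patient therefore has a screening TTS as well as a Day 1 TTS, and inclusion criterion d (Protocol 4.1) uses both. SAP 6.2.1 takes one value as baseline, the last before first dose. Screening TTS is not listed as a covariate.

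SAP 8.3.1.1 gives TS-CGI and the ADL subscale the same model, with their own baseline value as the covariate. The SAS code in SAP 8.2.1 and the content of SAP 8.2.2.2 (model sensitivity analyses) are redacted.

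**The concern.** With baseline as a main effect only, the model assumes that the regression of change on baseline is the same at week 2 as at week 12. Three of the five modelled visits (weeks 2, 4 and 6) fall in the 7-week titration, when doses are still rising. A slope that drifts over this time is plausible, though nothing in the documents shows it.

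With an unstructured covariance, the fitted common slope is a weighted average of the weekly slopes, and visits with small residual variance get most of the weight. If those are the early visits, the week-12 contrast is adjusted with a slope that suits week 2 better than week 12. What is at stake is part of the precision that baseline adjustment could give at the one visit that counts.

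**Working it through.** **The plan's own figure.** Protocol 9.1 states that "approximately 58 patients per arm will enable a power of at least 90" percent, for a "difference of 6.0 in the change from baseline to week 12 in TTS, assuming a standard deviation of 9.5 in each arm", "after accounting for potential dropouts". Allocation is 1:1. The number evaluable per arm is 2 × (1.960 + 1.282)² × (9.5/6.0)² = 52.7, so 53. An assumed 8% dropout gives 53/0.92 = 57.6, so 58. By the normal approximation, power is 92.5% at 58 and 90.2% at 53. The figure reproduces without any credit for covariates.

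**Formulas (complete data, large sample).** Let V be the residual covariance over the five weeks and b the vector of weekly slopes of change on baseline.
- Weights: w = V⁻¹1 / (1′V⁻¹1). Common slope: b* = w′b.
- Relative excess variance at week 12: (b₁₂ − b*)² × Var(baseline) / V₁₂.

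If all weekly slopes are equal, then b* = b₁₂ and the excess is zero whatever V is.

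**Illustration (all inputs assumed).** Baseline SD is 6.5. Residual SD rises linearly from 4.5 at week 2 to 9 at week 12, and the slope moves linearly from −0.10 to −0.40. The week-12 change SD is then √(81 + 0.16 × 42.25) = 9.37, close to the planned 9.5. The most that baseline can contribute at week 12 is 0.16 × 42.25/81 = 8.3% of residual variance. The loss depends on the residual correlation between visits, which also has to be assumed:

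| Residual correlation | Weight, weeks 2–6 | Weight, week 12 | b* | Excess variance | SE saved by week-specific slopes |
|---|---|---|---|---|---|
| Exchangeable 0 | 79% | 9% | −0.19 | 2.3% | 1.1% |
| Exchangeable 0.4 | 102% | −4% | −0.13 | 3.9% | 1.9% |
| Exchangeable 0.7 | 136% | −23% | −0.04 | 6.9% | 3.3% |
| Exchangeable 0.8 | 156% | −34% | +0.02 | 9.0% | 4.2% |
| AR(1) 0.5 | 83% | 10% | −0.17 | 2.8% | 1.4% |
| AR(1) 0.9 | 116% | −7% | −0.06 | 6.1% | 2.9% |

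Sums above 100% arise because later visits can take negative weight. For a difference of 6.0 at 58 per arm, normal-approximation power is 94.9% with week-specific slopes and 93.0% to 94.4% with the common slope.

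**Wider range.** A grid of 756 assumed covariance patterns held the week-12 change SD at 9.5. Baseline SD was 6 to 8, and the correlation of baseline with TTS was 0.7 to 0.9 at week 2 and 0.3 to 0.7 at week 12.
- Baseline by week lowered the week-12 SE by a median 1.4% (5th to 95th percentile 0.0% to 7.4%, maximum 11.8%). Power at 53 evaluable per arm rose by a median 0.7 points (0.0 to 3.6).
- Adding screening TTS as well (screening–baseline correlation 0.7 to 0.9) made this 3.2% (0.5% to 9.5%) and 1.5 points (0.3 to 4.7).

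**Simulation.** There were 6,000 trials per case at 53 per arm, with baseline SD 7. The correlation of baseline with TTS runs from week 2 to week 12 as shown. Entries are the week-12 SE.

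| Case | Unadjusted | Common slope | Week-specific | Plus screening |
|---|---|---|---|---|
| 0.8 to 0.4 | 1.846 | 1.791 | 1.757 | 1.749 |
| 0.8 to 0.5 | 1.839 | 1.823 | 1.823 | 1.818 |
| 0.8 to 0.3 | 1.841 | 1.725 | 1.653 | 1.651 |
| 0.6 throughout, constant SD | 1.850 | 1.853 | 1.857 | 1.816 |

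In the first case power is 91.8% with the common slope and 92.7% with week-specific slopes. Mean error was at most 0.04 points for every estimator. A separate simulation at 58 per arm gave a type I error of 5.2% for both models, and a cost of about 0.3 power points for the extra terms when the slope is constant.

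**Screening TTS.** If screening predicts week 12 as well as Day 1 does, R² rises from ρ² to 2ρ²/(1 + r), where r is the screening–baseline correlation. The illustration implies ρ = 0.6 × 6.5/9.8 = 0.40. With r from 0.7 to 0.9, residual variance falls by a further 3.3% to 1.0%. Screening can be up to 31 days before Day 1, so equal prediction is optimistic.

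**The case against.** The strongest reply is that this is a preference about efficiency and not an error. A common slope leaves the randomised contrast valid, and the simulations agree. The sample size rests on an SD of 9.5 with no stated covariate credit, and in the central case the 90% target is met under either model. The drift in slope is assumed, because the documents report no variances, correlations or slopes. In two of the four simulated cases week-specific slopes gained nothing. The redacted code may already contain the term, or SAP 8.2.2.2 may cover it.

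All of this stands, and it limits the point to a conditional, low-priority one. What remains is that the visible text of both documents describes a single slope. Where slopes drift, the early visits dominate that slope, and the possible loss is larger than the cost of removing it.

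A reader might infer that week-12 precision is certainly lost, and for nothing. The documents do not support that: a constant slope means no loss, and the extra terms carry a small cost.

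**Conclusion.** The point holds as an efficiency remark. On the prose of both documents, one baseline slope serves weeks 2 to 12. If the true slope drifts, weeks 2 to 6 largely set it and the week-12 contrast loses some precision without bias.

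The typical size is about 1% to 3% of the SE, or about 1 to 2 power points. The lower end is baseline by week alone, and the upper end includes screening TTS. The loss is zero with a constant slope. The maximum of about 12% of the SE came only where the week-12 slope lay far from the early slopes or had the opposite sign. Every covariance input behind these figures is an assumption.

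A reader might also infer that the primary result would be biased or the trial underpowered. Neither follows. No bias or type I error inflation appeared, and 58 per arm reproduces from the plan's own inputs. Power below 90% at 53 evaluable arose only for assumed patterns that the documents give no reason to expect.

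**What to change.** Before unblinding, add baseline TTS by week to the fixed effects in SAP 8.2.1, and make the code match. If the redacted code already has the term, the prose should say so. Keep the endpoint as change from the Day 1 baseline.

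Use the same form in SAP 8.3.1.1 with each endpoint's own baseline value. TS-CGI gains four parameters. ADL gains one, since its only post-baseline visits are weeks 6 and 12. The gain was not calculated for these endpoints, so the reason there is consistency of form.

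The cost is one line of text and code and four extra parameters in the primary model, about 0.3 power points if the slope is truly constant. Screening TTS, also by week, is an optional second covariate with a smaller expected gain.

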### 8.2.2. Sensitivity Analysis

The primary efficacy analysis on change in the TTS at week 12 is to use MMRM model, described in Section 8.2.1 (the primary analysis model), using all observed data. This model is appropriate when data is missing at random (MAR). To assess the robustness of the primary efficacy analysis, the following additional analyses will include:

[REDACTED]

Details of sensitivity analysis for missing data and the statistical model are explained in the next 2 sections.

### 8.2.2.1. Sensitivity analyses for missing data

A large black rectangular redaction box covers the majority of the page content, from approximately y=113 to y=886. The redaction is irregular, with jagged edges and some white space visible at the top and bottom.

[REDACTED]

The complete multiple imputation methodology, along with SAS code, is detailed in Appendix C (Section 19.3).

#### 8.2.2.2. Sensitivity analysis for the statistical model

[REDACTED]

[REDACTED]

[REDACTED]

#### 8.2.3. Subgroup Analysis

Data summary of TSS of YGTSS by subgroup below will be conducted using the mITT population. In addition, 95% CI for the change from baseline will be provided:

- Gender: Male and Female
- Race Group: White, Black or African American, and Other
- Baseline Age Group (6-11 years, 12-16 years)
- CYP2D6 impairment status (Yes/No)

In addition, TTS of YGTSS will be analyzed in the same fashion as the primary analysis in Section 8.2.1 by baseline age group, with the exception that age group will not be included as the fixed effect.

### 8.3. KEY SECONDARY EFFICACY ENDPOINT(S) AND ANALYSES

Key secondary endpoints for this study are as follows:

1. Change in the TS-CGI score from baseline to week 12
2. Change in the TS-PGII score from baseline to week 12
3. Change in the C&A-GTS-QOL ADL subscale from baseline to week 12

A hierarchical (fixed-sequence) testing approach will be used for the analysis of the primary and key secondary endpoints to maintain the experiment-wise type I error rate of 5%. If an endpoint is

not statistically significant, confirmatory hypothesis testing will not be carried out on the remaining hypotheses, and remaining hypotheses will be considered exploratory rather than confirmatory.

Secondary efficacy analyses will be based on mITT analysis set.

### 8.3.1. Key Secondary Efficacy Analysis

#### 8.3.1.1. Analysis of the change in the TS-CGI and C&A-GTS-QOL ADL subscale

The change in the TS-CGI score from baseline to week 12 (1st secondary endpoint) and C&A-GTS-QOL ADL subscale score from baseline to week 12 (3rd secondary endpoint) will be analyzed in the same fashion as the primary analysis in Section 8.2.1, with the exception that the baseline value of the given endpoint will be included as the covariate.

